### 3.2.13 Seizure frequency

Seizure frequency per 28 days (SF) will be based on the number of days (D) for which seizure information was provided:

$$\text{SF} = (\text{Number of seizures in the analysis period}) \times (28/D)$$

If a seizure cluster is reported, it will be assigned to the correct seizure type and the highest recorded daily number of seizures of that seizure type during the 28 days prior to the cluster event will be used as the imputed number of seizures for the day on which the cluster occurred. If no other seizures are recorded for that seizure type for the subject in the 28 days prior to the cluster event, the frequency will be set to 1.

If more than 1 cluster event occurred on the same day for a Type II or Type III seizure, the seizure clusters will be assigned to the correct seizure type and the frequency for each cluster event will be set to the highest recorded daily number of seizures of that seizure type during the 28 days prior to the cluster event. If no other seizures are recorded for that seizure type for the subject in the 28 days prior to the cluster event, the frequency will be set to the number of cluster episodes reported.

If more than 1 cluster event occurred on the same day for a Type I seizure, the seizure clusters will be assigned to the correct seizure type and the overall frequency will be set to the maximum of:

- The highest recorded daily number of seizures of that seizure type during the 28 days prior to the cluster event
- The number of cluster episodes reported on that day

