### **3.2.15 Response to treatment**

Response to treatment is based on the percent change in seizure frequency relative to Baseline (using the Baseline definition in Section 3.3). Study participants who experience at least a 50% reduction from Baseline will be considered  $\geq 50\%$  responders. Study participants who experience at least a 75% reduction from Baseline will be considered  $\geq 75\%$  responders.

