### **3.3 Definition of Baseline values**

In general, Baseline will be defined as the last non-missing value collected prior to the first dose of LCM in the original study for rollover subjects and in SP848 for direct enrollers for safety and efficacy variables unless otherwise noted for a specific type of data. The Baseline value for seizure counts for directly enrolled study participants will be taken from the Historical Seizure Count CRF/eCRF module collected in SP848 in combination with the seizure diary data collected from the date of the Screening Visit to the day prior to the date of first dose of LCM.

For participants enrolling from EP0060 the baselines for the questionnaires will consider each EP0060 enrollment group separately, those are: ILL (Initiating intravenous lacosamide Group: not currently receiving LCM, i.e. LCM naïve), OLL (Open-label lacosamide Group: currently receiving oral LCM in open-label long term study), and RxL (Prescription lacosamide Group: currently receiving prescribed oral LCM from commercial supply, VIMPAT). For ILL group baseline will be Visit 1 from SP848, for OLL group baseline will come from SP848 using above baseline definition, and for RxL group there will be no baseline data as they were on oral LCM prior to EP0060.

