### 6.3.3 Historical seizure counts

The Historical Seizure Counts CRF/eCRF module records the number of seizures per pre-selected ILAE seizure code experienced by the subject during the 4 weeks prior to Baseline.

These data will be provided in a subject data listing. This will be summarized for the SS, by seizure classification subgroups.

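### Section 3.2.13 can score a seizure cluster as a single seizure, and the SAP does not say how clusters are counted in Baseline, so percent change and responder rates can be distorted among participants with clusters

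*SAP*

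**What the plan says.** Section 3.2.13 of the SAP scales the seizure count to 28 days over the diary days with information. For a reported cluster it looks back 28 days, and the highest daily count of that seizure type "will be used as the imputed number of seizures for the day on which the cluster occurred". If no other seizure of that type is on record "in the 28 days prior to the cluster event, the frequency will be set to 1".

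For two or more clusters on the same day the rule depends on type:
- Type II and III: "the frequency for each cluster event will be set to the highest recorded daily number of seizures of that seizure type" in the look-back window, so the day total grows with the number of clusters.
- Type I (partial-onset): "the overall frequency will be set to the maximum of" two quantities, the highest daily count in the look-back and the number of clusters that day.

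Baseline is built differently. Under Section 3.3, for direct enrollers it is "taken from the Historical Seizure Count CRF/eCRF module collected in SP848 in combination with the seizure diary data" from Screening up to the day before first dose. Section 6.3.3 says that the historical form "records the number of seizures per pre-selected ILAE seizure code experienced by the subject during the 4 weeks prior to Baseline". For rollover participants, Section 3.3 takes Baseline from before the first dose in the original study.

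Sections 3.2.14 and 3.2.15 turn these frequencies into percent change and ≥50% and ≥75% responder status. Section 10.1 plans no check of the cluster imputation.

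**The concern.** There are three problems in the rule and one gap around it.

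- A cluster is more than one seizure, so a value of one lies below any possible true size. An empty look-back is the ordinary situation of a participant whose seizures come mainly in clusters, and it becomes more common as isolated seizures become rarer.
- The imputed value is the number for the day. Read literally, it replaces seizures of that type recorded individually on that day.
- Type I days with several clusters are scored on a different principle from Type II/III days. Section 3.2.13 gives no reason, and the Amendment 2 log that introduced the split gives none either.
- A recalled 4-week total holds no daily numbers, so the look-back cannot be applied to it. The SAP does not say how clusters enter that total, or how they were scored in parent-study Baselines.

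Percent change therefore may compare two counts made in different ways. Three of the five secondary efficacy variables in Section 2.3.4.2 depend on it: percent change and the two responder variables.

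**Working it through.** The SAP states no figure for this rule, so there is nothing to reproduce. Its formulas are applied here to a participant whose seizures do not change.

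**Inputs.** From the SAP: SF = count × 28/D (3.2.13); PCH = (SF_T − SF_B)/SF_B × 100 (3.2.14); responder thresholds of 50% and 75% (3.2.15). Assumed, because the SAP gives neither: cluster size k and clusters per 28 days c.

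**1. Clusters only, Baseline at full size, treatment clusters scored 1.** PCH = (c − ck)/(ck) = 1/k − 1, whatever c is.

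| k | 2 | 3 | 4 | 5 | 10 |
|---|---|---|---|---|---|
| PCH | −50% | −66.7% | −75% | −80% | −90% |

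With c = 3 and k = 4: Baseline 12, treatment 3, (3 − 12)/12 = −75%. The SAP leaves open whether an earlier imputed cluster counts as a recorded daily number. Here it makes no difference, because the earlier value is also 1.

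**2. Clusters plus isolated single-seizure days (look-back maximum 1), same Baseline assumption.**
- 4 isolated + 2 clusters of 5: 14 → 6 = −57.1%.
- 4 isolated + 1 cluster of 5: 9 → 5 = −44.4%, not a responder.
- 4 isolated + 1 cluster of 3: 7 → 5 = −28.6%, not a responder.

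**3. Other Baseline assumptions.**
- Clusters scored 1 in both periods: 3 → 3 = 0%.
- One cluster scored 1 at Baseline and 5 on treatment: (5 − 1)/1 = +400%.

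**4. Several clusters on one day** (e clusters, look-back maximum m). Type I scores max(m, e); Type II/III scores e × m.
- e = 2, m = 5: 5 against 10.
- e = 3, m = 4: 4 against 12.
- e = 2, m = 1: 2 against 2, no difference.

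**5. Day total.** Suppose the look-back maximum is 2 and the day has 3 individually recorded seizures plus a cluster. Read literally, the day scores 2, below the 3 on record.

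**6. Simulation with no treatment effect** (28-day Baseline, 12 × 28 days of treatment, Poisson events, every participant having unquantified clusters). Entries are the percentage scored as ≥50% responders; the last column comes from a separate run.

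| Pattern per 28 days | Rule on treatment, full-size Baseline | True counts in both | Rule in both |
|---|---|---|---|
| 3 clusters of 4 | 84 | 8 | 7.8 |
| 2 clusters of 4 + 2 isolated | 61 | 8 | 4.7 |
| 1 cluster of 3 + 4 isolated | 20 | 6 | 3.8 |

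The inflation comes from the mismatch between periods. It disappears when the same rule scores both.

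**The case against.** A reader might infer that the undercount is one-sided and always flatters treatment. The documents do not support that. Section 3.2.13 speaks of any analysis period, Screening diary days are part of Baseline for direct enrollers, and nothing says that clusters in the 4-week count or in parent-study Baselines were entered at full size. A caregiver who cannot number a cluster in a daily diary may not recall an exact 4-week total either. The imputation can also overshoot: a true cluster of 3 following a day with 10 is scored 10. This stands, and it makes the direction of bias conditional.

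A reader might also take the Type I rule for an error. It was introduced deliberately in SAP Amendment 2. It never scores a day below its number of clusters, and participants with generalized seizures are assessed on seizure days (Section 10.1.5), which cluster size does not affect. What remains is an unexplained difference that bears on partial-onset frequency, the basis of the responder variables.

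Finally, the primary variables are safety variables, no primary efficacy variable exists, and Section 3.1 plans no hypothesis testing. Section 4.2.5 calls this an uncontrolled study with individualized dosing in which efficacy is not the primary objective. That limits the weight of the point but does not make a cluster of one seizure correct.

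**Conclusion.** The point holds in conditional form, as a should-fix. The rule can score a cluster day below the smallest possible cluster and, read literally, below that day's own record. It handles Type I and Type II/III differently without a stated reason, and the SAP does not fix how clusters are scored in Baseline.

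If Baseline clusters were counted nearer full size, percent change and both responder rates are inflated among participants with clusters. In the worked case an unchanged participant moves from 12 to 3, or −75%. If scoring is the same in both periods there is no such bias, and if the mismatch runs the other way the bias is towards worsening.

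The simulated 84% and 61% should not be read as study-level effects. They assume that every participant has unquantified clusters and a full-size Baseline. If 5% of participants (an assumption) fitted the first pattern, the overall ≥50% responder rate would shift by about 0.05 × (84 − 8) = 3.8 percentage points. Seizure-free status is unaffected, because a cluster always counts as at least one seizure. No error rate is at stake, only the reported descriptive figures.

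**What to change.** 1. In Section 3.2.13, set the day total for a cluster day to no less than the larger of 2 and the number of seizures of that type individually recorded that day.
2. State how clusters are scored in the historical 4-week count and in parent-study Baselines, and use the same scoring in both periods where the data allow.
3. Report the number of participants with imputed cluster days. Add one sensitivity table of percent change and responder rates that either excludes those participants or varies the imputed cluster size, for example from 2 to 5, with Type I clusters also summed as for Type II/III.

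Item 1 alone is not enough. In the worked case a floor of 2 gives 3 × 2 = 6 against 12, which is −50% and still a ≥50% response. Letting the size run over 2, 3, 4 and 5 gives 6, 9, 12 and 15, that is −50%, −25%, 0% and +25%. That spread is what the table would show the reader.

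The cost is SAP wording, a small derivation change and one extra table. Responder rates may come out slightly less favourable.

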### **3.2.14 Percent change in seizure frequency**

The percent change in seizure frequency per 28 days (PCH) from the Baseline value (B) (using the Baseline definition in Section 3.3) to the Treatment Period interval (T) is defined as:

$$PCH = [(SF_T - SF_B) / SF_B] \times 100$$

where  $SF_T$  corresponds to the seizure frequency during the Treatment Period for the relative interval in the open-label study and  $SF_B$  corresponds to the Baseline seizure frequency. The frequency for both periods will be standardized to the number of seizures per 28 days.

### **3.2.15 Response to treatment**

Response to treatment is based on the percent change in seizure frequency relative to Baseline (using the Baseline definition in Section 3.3). Study participants who experience at least a 50% reduction from Baseline will be considered  $\geq 50\%$  responders. Study participants who experience at least a 75% reduction from Baseline will be considered  $\geq 75\%$  responders.

### **3.2.16 Seizure day**

A seizure day is defined as a day where any type of seizure was reported in the seizure diary and seizures were assessed. Days in the seizure diary which are marked as “not done” on the CRF/eCRF will not be counted as a seizure day.

### **3.2.17 Seizure-free day**

A seizure-free day is defined as a day where no seizures were reported in the seizure diary and seizures were assessed. Days in the seizure diary which are marked as “not done” on the CRF/eCRF will not be counted as a seizure-free day.

### 3.2.18 Seizure-free status

Study participants will be considered seizure-free for a given period if the subject completes the period, reports zero seizures during the period, and have no more than 10% of days in the period for which seizure data is not available (ie, “not done” is noted on the Seizure Frequency CRF/eCRF module). Seizure diary days where “not done” has been reported for days when study participants were participating in a previous study will not be counted toward the 10% of days with missing seizure diary data (eg, missing seizure data due to a previous study will not count against a subject in the assessment of seizure-free status). If a subject enrolls in the EP0060 study, days of participation in EP0060 will also not be considered in the assessment of seizure-free status.

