#### **2.4.1.2 Study participants enrolling directly into SP848**

Beginning with Protocol Amendment 4, at selected sites, up to approximately 100 eligible pediatric study participants  $\geq 4$  years to  $\leq 17$  years of age with partial-onset seizures (deemed appropriate for treatment with adjunctive LCM) who have not previously received LCM will be permitted to enroll directly into SP848.

Beginning with local Protocol Amendment 5.2 for sites in Japan, approximately 46 eligible pediatric subjects  $\geq 4$  years to  $\leq 17$  years of age with partial-onset seizures who have not previously received LCM will be permitted to directly enroll at approximately 9 sites in Japan. Beginning with Protocol Amendment 5.4 for sites in China, approximately 60 additional eligible pediatric subjects with partial-onset seizures aged  $\geq 4$  years to  $\leq 17$  years, who have not previously participated in a LCM clinical study, will directly enroll into SP848.

Subjects who enroll directly into SP848 without previous participation in a LCM clinical study will undergo screening. Eligible subjects will initiate treatment with LCM, and the LCM dose will be titrated to a level to optimize tolerability and seizure control. Subjects will be able to

receive LCM oral solution or LCM tablets for up to 2 years as determined appropriate by the investigator.

SP848 includes subjects  $\geq 1$  month to  $\leq 18$  years of age since subjects who complete SP847 or another applicable LCM pediatric epilepsy study in subjects  $< 18$  years of age may have aged to 18 years old by the time they complete that study and enroll in SP848.

The same study conditions described in Section 2.4.1.1 (e.g., minimum and maximum LCM dose, required office visits for dose increases, concomitant AEDs, and LCM taper) also apply.

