### **3.2.3 Mapping of assessments performed at Early Termination Visit**

Safety and efficacy assessments at an Early Termination Visit (ETV) that correspond to a scheduled visit will be summarized at the scheduled visit corresponding to the ETV if the assessment was scheduled to occur at that visit. Such assessments will also be considered for Last Visit. Study participants who prematurely discontinue the study will be evaluated based on the data collected at each visit attended. For those study participants the ETV will be mapped to the next scheduled visit, ie, the assessments documented at Visit 13/ETV will be assigned to the next scheduled visit, for which the corresponding assessment is scheduled, following the last documented visit.

In particular, assessments which are done at all visits during the Treatment Period (eg, vital signs, body weight and height), will have ETVs corresponding to a scheduled visit mapped to the corresponding scheduled visit.

For study participants enrolled from sites in Japan, they are allowed to stay in the study longer than 2 years. Such study participants will have a separate ETV if they are in the study after Visit 13.

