### 3.2.5 Monthly time intervals

A month is defined as 28 days and time intervals based on monthly durations are defined as multiples of 28 days (eg, 12 months is defined as 336 days). A subject is included in the analysis for a 3-month interval if they are exposed to LCM at any time during that time interval.

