### 3.2.21 Seizure time intervals

Study participants will be classified as belonging to one of the following time intervals for the purpose of seizure efficacy analyses:

- $\leq 3$  months
- $> 3$  to  $\leq 6$  months

- >6 to ≤12 months
- >12 to ≤18 months
- >18 to ≤24 months
- >24 to ≤30 months
- >30 to ≤36 months
- >36 to ≤42 months
- >42 to ≤48 months
- >48 months

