### 10.1.6 Seizure-free status

The number and percentage of study participants achieving a seizure-free status (as defined in Section 3.2.18) will be presented for overall treatment period. This will be presented by completer cohorts (as defined in Section 3.2.19).

The number and percentage of study participants seizure-free among completer cohorts (as defined in Section 3.2.19) will also be presented separately by seizure type (simple partial, complex partial, secondarily generalized) for subjects with POS.

Seizure-free status will also be presented by seizure time intervals (as defined in Section 3.2.21). The number and percentage of study participants with seizure-free status at the end of each time interval during the treatment period will be presented separately by seizure type (simple partial, complex partial, secondarily generalized) for POS.

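### Seizure-free status by time interval requires completing the interval but has no stated denominator, so planned study end at 2 years can lower the percentage after month 24

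*SAP*

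**What the plan says.** **Who counts as seizure-free.** SAP Section 3.2.18: "Study participants will be considered seizure-free for a given period if the subject completes the period, reports zero seizures during the period". It adds a limit of 10% on days without seizure data.

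**Where the rule is used.** Section 10.1.6 applies it to the overall Treatment Period and to completer cohorts, and then adds: "Seizure-free status will also be presented by seizure time intervals". The intervals, listed in Section 3.2.21, include ">24 to ≤30 months" and end with an open interval beyond 48 months.

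**The calendar.** Section 3.2.5 sets a month at 28 days.

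**Length of treatment.** Section 2.4.1.2 lets direct enrollers receive "LCM oral solution or LCM tablets for up to 2 years". Section 3.2.3 names one exception: "For study participants enrolled from sites in Japan, they are allowed to stay in the study longer than 2 years". Section 2.4.1.1 gives no length for rollover participants, but naming only Japan implies that the 2-year limit applies to them elsewhere.

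**The denominator.** Section 10.1.6 gives none for the by-interval table. The nearby rules are:
- Section 10: efficacy variables are summarized for the Full Analysis Set.
- Sections 10.1.2 and 10.1.3 (and 10.1.4 by reference): anyone with seizure data in the interval is included.
- Section 3.2.5: "A subject is included in the analysis for a 3-month interval if they are exposed to LCM at any time during that time interval".
- Section 3.1: percentages use whatever number of participants suits the analysis.

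**The concern.** The numerator demands completion of the interval. Nothing says that the denominator is limited to people who could complete it. After month 24, most participants outside Japan reach their planned end inside an interval that runs to day 840. A child with a full diary and no seizures up to the planned last day would then be counted among those not seizure-free, for an administrative reason.

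The by-interval table is where a reader would look for the time course of seizure freedom. A drop just after month 24 caused by planned follow-up ending could be read as loss of effect. Two programmers working from the same text could also produce very different tables.

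**Working it through.** **Inputs**
- Month = 28 days (Section 3.2.5).
- Interval: above 24 and up to 30 months (Section 3.2.21).
- Planned treatment: up to 2 years outside Japan (Sections 2.4.1.2 and 3.2.3).
- About 46 planned direct enrollers in Japan and up to about 400 participants in all (Section 2.5).
- Not in the SAP: the week of Visit 13, the number treated past day 840, and the true seizure-free percentage.

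**Step 1: the plan's own figure.** 12 × 28 = 336 days, as Section 3.2.5 states.

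**Step 2: interval bounds.** 24 × 28 = 672 and 30 × 28 = 840. The interval is days 673 to 840, which is 168 days.

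**Step 3: where 2 years ends**
- 2 × 365.25 = 730.5 days. Time in the interval: 730.5 − 672 = 58.5 days, or 58.5/168 = 34.8%. Shortfall: 840 − 730.5 = 109.5 days.
- 104 weeks = 728 days. Time in the interval: 56 days, or 33.3%. Shortfall: 112 days.
- If the 2 years were scheduled as 96 weeks (assumption), treatment would end on day 672 with no time in the interval, apart from any titration time, visit window or taper.

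On a calendar reading of 2 years, the participant enters the interval and cannot complete it.

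**Step 4: what each possible denominator does**
- *Full Analysis Set:* 2-year participants are counted and cannot succeed. Everyone who left earlier is counted as well. Artefact present.
- *Anyone with seizure data in the interval:* 2-year participants are counted and cannot succeed. Artefact present.
- *Only those who completed the interval:* no artefact. The text does not state this, and it would also remove participants who discontinued within the interval.

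**Step 5: size, as an illustration.** Let p be the true seizure-free proportion, assumed equal in those who continue and those who stop, and let s be the share of the denominator treated through day 840. Then shown percentage = p × s.

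| s | true 20% shown as | true 40% shown as |
|---|---|---|
| 0% | 0% | 0% |
| 11.5% (46/400) | 2.3% | 4.6% |
| 25% | 5% | 10% |
| 50% | 10% | 20% |

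The share 46/400 uses planned figures from Section 2.5 and assumes that all 46 continue and no one else does. The other shares and both values of p are assumptions.

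**Step 6: the last interval.** An interval beyond 48 months has no upper bound, so completing it has no meaning. This needs no assumption about the denominator.

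**Step 7: the other displays.** The 30-month completer cohort in Section 3.2.19 requires at least 840 days of treatment, so a 2-year participant is not in it. The overall Treatment Period ends with the participant's own last dose or termination visit. Neither display has this artefact.

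**The case against.** A reader might infer that the plan guarantees a collapse of seizure freedom after month 24. The documents do not support that, for four reasons.

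- **The denominator is unstated.** The inclusion rule in Section 3.2.5 is worded for 3-month intervals, and this one is 6 months long. The rule on any seizure data is written for percent change and responders. Section 10.1.6 also speaks of status at the end of each interval, which could suggest a denominator of those who reached that end. This stands: the fall follows from the two most natural readings, but it is not written down.
- **Entry depends on a schedule that is not shown.** Two years is a maximum, and a 96-week schedule would end at day 672. This stands as a limit on the size.
- **The fall would not be total.** Participants in Japan, and anyone else treated through day 840, can still qualify. This stands.
- **The table is supplementary.** Section 2.3.4.3 confines the secondary analyses to the overall Treatment Period and lists presentation by time interval as something that may be added among the other efficacy variables. The completer-cohort display already gives a view of durability without the artefact, and the study is descriptive throughout. This stands. It rules out saying that a secondary efficacy result is distorted.

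These points limit the importance but do not repair the text. Of the candidate denominators, the two that the SAP uses elsewhere for efficacy both give the wrong result, and the one that avoids it appears nowhere for this table. The gap in the last interval is untouched by any of them.

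**Conclusion.** The point holds as a defect in one supplementary table. A numerator that depends on completing the interval is paired with an open denominator. On the Full Analysis Set or any-seizure-data reading, the seizure-free percentage after month 24 is pulled down by planned study end and not by seizures. For the interval beyond 48 months, the rule cannot be applied at all.

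The size is not known. It depends on how many participants continue past day 840 and on when Visit 13 falls. If 0% to 50% of the denominator continues, a true 20% would appear as 0% to 10%, given equal seizure freedom in those who continue and those who stop. If 2 years means 96 weeks, few participants would enter the interval, and on the any-seizure-data denominator the effect would be small. The change is still worth making, because it is cheap and removes a reading that could pass for loss of effect.

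**What to change.** In Section 10.1.6, for the by-interval table:

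- Limit each interval's denominator to participants whose planned follow-up reaches the end of that interval. All participants limited to 2 years are then left out of the 24-to-30-month column, whether they completed or discontinued.
- Count participants with follow-up planned through the interval who discontinue within it as not seizure-free.
- Show the numbers entering, eligible for and completing each interval.
- Leave seizure-free status out for the interval beyond 48 months, or split that interval into closed 6-month intervals.
- Say how planned follow-up is determined for Japan, where the current text gives no fixed length.

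Eligibility must follow planned follow-up and not outcome. Removing only those who completed as planned, while keeping those who discontinued, would let 2-year participants enter the 24-to-30-month column only as failures.

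The cost is a few lines of SAP text and a participant-level flag built from data already collected. The downside is a smaller denominator in the late intervals.
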